8.3. Explantations

In the short term, explantations will usually occur due to acute/chronic infection, instability, and/or subject experiencing severe pain due to various causes. Reduced mobility alone, if it occurs, is typically not a predominant factor in prompting revision surgery. Long-term, aseptic loosening and/or severe pain may become a determining factor as to whether to proceed with device revision. Reasons for removal are not limited to these circumstances alone. The Sponsor requests Investigators to return any revised R3 Hip System components for retrieval analysis.

Explanted components are sterilized by steam autoclave or other appropriate sterilization method according to the Institution's standard sterilization procedures. Only properly packaged explants should be shipped, and the Sponsor notified before any shipment. If possible, the Sponsor will collect histological (bony ingrowth quality, bone quality, response to potential wear debris, etc.) and metallurgical (metal wear, deformation, cracking, corrosion, etc.) information from explants. For all explants, the investigator must record and forward a description of intra-operative findings including: 1) presence of

wear debris, 2) what types of hip components are being replaced, 3) and intraoperative findings relating to the device failure. Explant analysis will occur through the duration of this study.

It should be noted that the Sponsor is not always able to retrieve known explants. Some surgeons may refuse to return explants, and some institutions/hospitals will not release explanted component(s) due to their "policies."

9. Statistical Methods

Evaluations after database closure will be performed on an Intention to Treat (ITT) basis. The analysis will include the descriptive statistics of patient demographics and baseline characteristics. Accountability data will include the number of patients enrolled and the follow-up data collected. Data will be analyzed for changes from preoperative at 3 months, 1 year, 3 years, 5 years, 7 years and 10 years. Safety will be assessed by identifying and summarizing device-related adverse events throughout the study. Analysis of the success rate will be performed using Kaplan-Meier (KM) Survival Analysis. The KM estimate of the success rate along with the 95% confidence interval of the estimate will be included in the final report.

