2. STUDY OBJECTIVES

The primary objective of this phase of this study is to confirm that the safety and effectiveness of the R3 Biolox delta Ceramic Acetabular System (DOD) is maintained in the long term (to 10 years).

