Smith & Nephew Orthopaedics is the sponsor of a prospective, multicenter, non-randomized, clinical outcomes study of the R3 delta Ceramic Acetabular System in patients with degenerative hip disease in Europe. The study was designed to evaluate the performance of the R3 cup with multiple articulation couples including the Biolox delta ceramic-on-ceramic (DOD) and the Oxidized Zirconium-on-crosslinked polyethylene (OxZr/XLPE) articulation couple. The study devices were commercially available in Europe at that time, and the study satisfied EU post-market surveillance requirements. The study was conducted in compliance with ISO 14155 and International Conference on Harmonization Good Clinical Practice (ICH GCP) Guidelines (Notes for Guidance on GCP CPMP/ICH/135/95); National Statement on Ethical Conduct in Research Involving Humans, consisting of a series of Guidelines made in accordance with the National Health and Medical Research Council Act 1992; World Medical Association Declaration Of Helsinki - Ethical Principles for Medical Research Involving Human Subjects October 2008; and 21 CFR 812 revised April 1st, 2008 (Medical Devices), as well as with all applicable local laws and regulations.

2. Study Objectives

The primary objective of this phase of this study is to confirm that the safety and effectiveness of the R3 Biolox delta Ceramic Acetabular System (DOD) is maintained in the long term (to 10 years).

3. Study Design

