3.5.2 Secondary efficacy endpoints

Secondary endpoints will be evaluated at 10 years post study procedure and include the following:

- Patient outcomes as measured using the modified Harris Hip Score;;
- Radiographic evaluation to assess radiographic success defined as:
 - -No radiolucencies greater than 2 mm in 50% or more in any of the cup or stem zones; and
 - -No femoral or acetabular subsidence greater than or equal to 5mm from baseline; and
 - -No acetabular cup inclination changes greater than 4 degrees (4°);

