4.4 Handling of missing and incomplete data

The number of patients with missing data will be presented under the "Missing" category, if present.

When continuous data are being summarized, only the non-missing values will be evaluated for computing summary statistics.

A sensitivity analysis will be carried out comparing results of the original analysis to the results of an analysis where all missing data are assumed to be failures.

A second sensitivity analysis will be carried out using multiple imputation of the missing data in the form of a tipping point analysis. Multiple scenarios will be analyzed, each with a different number of missing data points imputed as successes for each treatment group. (Missing data points not imputed as successes will be imputed as failures.) The purpose of the analysis is to find the tipping point where a certain number of success imputations for each treatment group causes the inference to reverse.

In general, partial dates will be imputed as follows:

- if only the day is missing, the first day of the month will be assumed;
- if the day and the month are missing, January 1st will be assumed;
- if a date is completely missing or unknown the patient's data will not be included for analysis

Protocol Number: TBD Version 0.3

Forms							
Title	Title Statistical Analysis Plan Template						
Co	Code Version Effective Date Page						
FRM_S	FRM_ST03_032 0.3 23 Apr 2015 9 of 12						

5. Evaluation of Demographic and Baseline Characteristics

Given the nature of this study, the demographic data have been already obtained. The demographic and baseline characteristics will be summarized using descriptive statistics for the Enrolled Set.

6. Patient Accounting

Patient accounting will be presented according to the recommendations in the FDA guidance entitled "Clinical Data Presentations for Orthopedic Device Applications".

- Actual A: Subjects with complete data for the primary endpoint, evaluated per protocol, in the window time frame.
- Actual B: Subjects with any follow-up data reviewed or evaluated by investigator ("all evaluated" accounting).
- Theoretical: Number of subjects that would have reached the beginning of the study window associated with each visit if all subjects returned.
- Deaths: Cumulative number of subjects that died during or prior to the study visit.
- Failures: Cumulative number of subjects that failed (revision) during or prior to the study visit.

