7.2 Analysis of secondary efficacy endpoints

Secondary endpoints include the following:

- Patient outcomes as measured using the modified Harris Hip Score;
- Radiographic evaluation to assess radiographic success defined as:
 - -No radiolucencies greater than 2 mm in 50% or more in any of the cup or stem zones; and
 - -No femoral or acetabular subsidence greater than or equal to 5mm from baseline; and
 - -No acetabular cup inclination changes greater than 4 degrees (4°) and

These endpoints will be summarized using descriptive statistics and presented for all post-operative visits.

8. Evaluation of Safety

The number of AEs, SAEs, USADEs, Reoperation and Revisions, and the number and the percentage of patients experiencing AEs, SAEs, USADEs will be presented for the enrolled set.

The number of AEs and the number and the percentage of patients with at least one AE will be presented for AEs, and SAEs.

The number and the percentage of patients with at least one AE will be presented by severity, seriousness, device relatedness and procedure relatedness.

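### The post-approval study aims to confirm that effectiveness is maintained to 10 years, but the SAP reports the modified Harris Hip Score only as visit-level scores, with no within-subject change

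*Combined protocol and SAP*

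**What the plan says.** The PAS addendum (section 2) and SAP section 2 set the primary objective: to "confirm that the safety and effectiveness of the R3 Biolox delta Ceramic Acetabular System (DOD) is maintained in the long term (to 10 years".

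mHHS is a secondary endpoint. SAP 3.5.2 states: "Secondary endpoints will be evaluated at 10 years post study procedure and include the following". The mHHS item in the list that follows reads only "Patient outcomes as measured using the modified Harris Hip Score". On analysis, SAP 7.2 says: "These endpoints will be summarized using descriptive statistics and presented for all post-operative visits". SAP 4.4 adds that "only the non-missing values will be evaluated for computing summary statistics", and addendum 9.1 likewise works from available records. SAP 4.1 promises 95% confidence intervals for secondary endpoints.

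None of these sections names a change score, a reference visit, a responder threshold or a longitudinal model for mHHS. In the same SAP section, two of the three radiographic criteria (subsidence and cup inclination) are defined as change within the patient.

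Section 9 of the main protocol is different. It states: "Data will be analyzed for changes from preoperative at 3 months, 1 year, 3 years, 5 years, 7 years and 10 years", and it plans multiple imputation for missing data. Neither provision appears in the PAS addendum's statistical section or in the SAP's plan for mHHS. The SAP mentions multiple imputation only for a tipping-point analysis of successes and failures.

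**The concern.** Whether function is maintained is a question about the same hips at two times. The planned summary compares whoever had a score at 3 years with whoever had one at 10 years. Subjects who do not return may be telephoned, but the Missed Visit/Telephone Follow-up form asks about component removal, problems with the hip, expected removal, satisfaction and willingness to repeat surgery. It has no mHHS, so these subjects leave the later means.

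If those who stay away differ in function from those who attend, the series of means moves for reasons of composition alone. A flat series could then conceal a decline among the subjects still attending, and a falling series could suggest a decline that no individual had. The planned output cannot separate these cases. What is at stake is how the 10-year functional result is interpreted. The primary endpoint, implant survivorship, is not affected.

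**Working it through.** **Cohort size.** The plan's figure reproduces: 137 − 1 death − 1 revision = 135 eligible subjects (addendum 9.2, SAP 3.3). The documents give no expected attrition, no mHHS standard deviation (SD) and no margin for decline. Every further input below is an assumption.

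**Composition shift.** Suppose all subjects have a 3-year score. Let q be the fraction without a 10-year score, A the 3-year mean of those who later attend at 10 years, and A − d the 3-year mean of those who do not.

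- 3-year mean, all subjects: (1 − q)A + q(A − d) = A − qd
- 10-year mean if no attender changes: A
- Apparent change: A − (A − qd) = +qd
- If attenders truly decline by δ, the apparent change is −δ + qd

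| q (of 135) | d = 5 | d = 10 |
|---|---|---|
| 15% (about 20 subjects) | 0.75 | 1.5 |
| 30% (about 40 subjects) | 1.5 | 3.0 |

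If non-attenders are the better-functioning subjects, d is negative and the same shifts go downward.

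**Against sampling error.** With 30% missing, n ≈ 0.70 × 135 ≈ 94. For an assumed SD of 12 to 16, the 95% half-width of the visit mean is 1.96 × SD/√n, or 2.4 to 3.2 points. The shift is thus about the size of the interval or smaller, but the interval does not reflect it.

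**Comparison of estimators.** The simulation assumed SD 14, a correlation of 0.6 between the 3-year and 10-year scores, a true change of −4.0, and a correlation of 0.5 between the tendency to attend and the score that drives dropout (lower scorers leave). "Visit means" is the 10-year attender mean minus the 3-year mean of all subjects.

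| Dropout follows | Missing | Visit means | Paired completers | Model or imputation under missing at random |
|---|---|---|---|---|
| 3-year score | 20% | −2.5 | −5.0 | −4.0 |
| 3-year score | 30% | −1.9 | −5.4 | −4.0 |
| 3-year score | 40% | −1.3 | −5.8 | −4.0 |
| 10-year score | 20% | −1.5 | −3.0 | −2.3 |
| 10-year score | 30% | −0.5 | −2.6 | −1.7 |
| 10-year score | 40% | +0.5 | −2.2 | −0.9 |

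In these scenarios the visit means are furthest from −4.0 in every row. The paired completer change is not unbiased either: it overshoots when dropout follows the 3-year score (regression to the mean among those retained) and undershoots when it follows the 10-year score. The model is right in the first case. In the second it falls further short than the paired change.

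**Whether the existing sensitivity analyses help.** SAP 4.4 plans one analysis counting all missing data as failures, and a tipping-point analysis imputing successes and failures by treatment group until the inference reverses. Both need a success/failure outcome. mHHS has no cut-off, and the PAS has one group and no formal test (SAP 3.5.1). Neither analysis can be run on mHHS as defined.

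**The case against.** The strongest reply is that the PAS is descriptive. SAP 3.5.1 says it is intended to document DOD survivorship, with no formal hypothesis test, and no decision rule turns on mHHS. That stands. A reader might infer that the study must demonstrate maintained function; the documents say only that it aims to confirm it. A descriptive study still has to describe the quantity that its objective names.

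Second, DOD subjects belong to the parent study, whose section 9 covers change from pre-operative and multiple imputation. This is partial cover. It promises no separate DOD result and no change from year 3, and the SAP's non-missing rule differs from it. The SAP is silent on change scores; it does not exclude them. SAP section 5 may also bring in the pre-operative score as a baseline characteristic, though it does not say so.

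Third, attrition is visible: SAP 4.4 and section 6 report missing counts, follow-up rate and reasons for discontinuation. That shows how many are missing, not how their function compared.

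Fourth, a reader might infer that the means will be too favourable because poorer hips drop out. The documents do not support a direction. The missed-visit form lists illness and difficult travel, but also patients who feel well and decline examination, holidays and business commitments.

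**Conclusion.** The point holds as a mismatch between the objective and the analysis of a descriptive secondary endpoint. As written, the mHHS output cannot distinguish change within patients from change in who attends. Neither the SAP 4.4 sensitivity analyses nor the parent protocol's section 9 closes the gap for the DOD cohort.

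The size is illustrative: 0.75 to 3.0 points, in either direction, for assumed q of 15–30% and |d| of 5–10. If visits are nearly complete, or if those who miss them do not differ, the shift is close to zero. The documents do not show that a decline will be hidden, and they give no margin against which to call the shift important.

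It might also be inferred that a paired change would settle the matter. At 30% missing it gave −5.4 or −2.6 against a true −4.0, so it is useful support but not a complete remedy.

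**What to change.** Amend SAP 3.5.2 and 7.2 to:

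- add within-subject mHHS change from pre-operative and from year 3, at 5, 7 and 10 years, with 95% confidence intervals;
- estimate it by a repeated-measures model or multiple imputation using all subjects' earlier scores, in line with section 9 of the main protocol;
- report the paired completer change as supportive output;
- tabulate the 3-year mHHS of subjects with and without a 10-year score;
- keep the visit-level means as descriptive output.

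The text should also say how scores after revision or death are treated in the model, since addendum 7.2 ends participation at revision.

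The cost is SAP wording, a model and a few tables. The SAP schedule marks mHHS up to the 3-year visit as already collected, so no visit or patient burden is added. There are two statistical downsides: the model relies on a missing-at-random assumption, and the completer result has a smaller n and possible selection bias.

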8.1 Adverse Event (AE)

An AE is any untoward medical occurrence, unintended disease or injury, or untoward clinical signs (including abnormal laboratory findings) in subjects, users or other persons, whether or not related to the study medical device.

8.2 Serious Adverse Event (SAE)

A SAE is any adverse event that:

Protocol Number: TBD Version 0.3

Forms					
Title	Title Statistical Analysis Plan Template				
Co	ode	Version	Effective Date	Page	
FRM_ST03_032		0.3 23 Apr 2015		11 of 12	

- resulted to death,
- was life threatening (at the time of the event); or
- resulted in hospitalization (initial or prolonged); or
- resulted in a disability or permanent damage (a significant, persistent or permanent change, impairment, damage or disruption in the patient's body function/structure, physical activities and/or quality of life);or
- resulted in a congenital anomaly or birth defect; or
- required medical or surgical intervention to preclude permanent impairment of a body function or prevent permanent damage to a body structure; or
- does not fit the other outcomes above, but may jeopardize the subject and may require medical or surgical intervention (treatment) to prevent one of the other outcomes.

Planned hospitalization for a pre-existing condition, or a procedure required by the protocol, without serious deterioration in health, is not considered a serious adverse event.

8.3 Adverse Event Relatedness to Study Device and Study Procedure

All adverse events (AE) are assessed for relatedness to the study device and study procedure based upon the following definition:

- Unrelated: the event is clearly not related to the study device or study procedure
- Possible: the event may or may not be related to the study device or study procedure. A relationship cannot be ruled out.
- Probable: the event is likely related to the study device or study procedure. A relationship cannot be ruled out.
- Definite: the event is clearly related to the study device or study procedure.

8.4 Unanticipated Serious Adverse Device Effect (USADE)

Any serious adverse effect on health or safety or any life-threatening problem or death caused by, or associated with, a device, if that effect, problem, or death was not previously identified in nature, severity, or degree of incidence in the investigational plan or application (including a supplementary plan or application), or any other unanticipated serious problem associated with the device that relates to the rights, safety, or welfare of subjects.

8.5 Reoperation and Revisions

Protocol Number: TBD Version 0.3

Forms					
Title	Title Statistical Analysis Plan Template				
Code		Version	Effective Date	Page	
FRM_ST03_032		0.3	23 Apr 2015	12 of 12	

A reoperation is any surgical procedure of the study hip. A revision is a surgical procedure of the study hip where one or more of the study components are removed and replaced with new implants.

All reoperations and any component revisions should be documented on the Adverse Event CRF.

8.6 Assessment of Adverse Event Severity

The Investigator will assess and categorize AEs as mild, moderate or severe based on the following definitions:

- Mild: the subject is aware of the sign or symptom, but finds it easily tolerated. The event is of little concern to the subject and/or little clinical significance. The event is not expected to have any effect on the subject's overall health or wellbeing.
- Moderate: the subject has discomfort enough to cause interference with or change in usual activities. The event is of some concern to the subject's health or wellbeing and may require medical intervention and/or close follow-up.
- Severe: the adverse event interferes considerably with the subject's usual activities. The event is of definite concern to the subject and/or poses substantial risk to the subject's health or well-being. The event is likely to require medical intervention and/or close follow-up and may be incapacitating or life threatening. Hospitalization and treatment may be required.

9. Protocol violations

A protocol deviation is an instance of failure, intentionally or unintentionally, to follow the requirements of the protocol. Protocol deviations include, but are not limited to: study visits outside the window or missed, failure to capture patient reported outcomes using the Modified Harris Hip Score (mHHS) at defined time points, failure to conduct radiologic evaluation at defined timepoints, failure to collect adverse events at defined time points, and failure to withdraw subjects defined by protocol withdrawal measures.

A listing of protocol deviations will be provided.

Protocol Number: TBD Version 0.3

Smith & Nephew - Advanced Surgical Devices Division

PROTOCOL APPROVAL FORM

Study Title:	A prospective, multicenter, non-randomized, clinical outcomes study of the R3\(\rangle\) Acetabular System in patients with degenerative hip disease	
Protocol Number:	R3H01/02/01/2017/Version 2.0 /BNA (including Post-Approval Study of the R3 Biolox delta Ceramic Acetabular System – Europe)	
Protocol Date:	February 01, 2017	
Protocol Version:	2.0	
Documents Attached:	☐ Initial Study Protocol x Amended Study Protocol	
Author (Name/Role):	[name] /CSM	

Approver Name	Approver Signature	Date Approved
[name]	3.02	20.02.2017

Smith & Nephew - Advanced Surgical Devices Division

PROTOCOL APPROVAL FORM

